***Telephone Screening-Part 2: Self-Report of Cognitive Impairment:***

Part-2 involves a second broad screening of cognitive function based on the Functional Independence Measure (FIM) completed by telephone interview. This incremental cognitive screening approach will circumvent potential diluting effects of including Veterans at extremes of the functional impairment continuum (mild, severe). For the 6-months prior to screening, Veterans requiring minimal or moderate assistance on problem-solving (scores: 3 or 4) and/or minimal assistance or supervision on memory (scores: 4 or 5), will remain eligible. These cut-off points are based on recent research by the study team^6 indicating that Veterans with these scores for these items most likely have short-term memory issues, impeding function, but not long-term memory issues. Veterans and/or healthcare surrogates will be asked to report location of any non-VA emergency room (ER), intensive and post-acute care treatment and for consent to collect these medical records for further screening.

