## **2.0 Introduction**

Each year, 15,000 Veterans incur a new ischemic stroke (stroke) with many of the survivors (32% - 56%) experiencing persisting cognitive impairments  and continued cognitive degradation.  For the more than 40,000^3 service members with moderate to severe TBI, the rates are similar with about 65% experiencing long-term cognitive impairments.  Considering the high prevalence of persisting cognitive impairments and that standard stroke and TBI rehabilitation have limited impact in mitigating this fundamental barrier to daily function, this protocol tests the scalability of an approach to effectively and feasibly tailor iTBS and APT to a Veteran's level of cognitive impairment.

Considering that Veterans with the same neurologic diagnosis are not homogenous by brain pathology or recovery patterns  and further that Veteran-specific factors such as level of cognitive impairment influence recovery,  studying treatment responsiveness by diagnosis alone is unlikely to advance understanding of how to tailor interventions to maximize each Veteran's daily function. Thus, we apply our recent work  and ideas from the field of mental health  to pilot transdiagnostic sampling. More specifically, we create a sample of Veterans with either TBI or stroke who are linked across diagnoses by homogeneous levels of cognitive impairment. Applying our recent work,  we use the Functional Independence Measure (FIM) to broadly link Veterans according to the FIM category of moderate cognitive impairment. This category includes individuals with short-term memory problems requiring assistance for problem solving and shifting attention. As this is a broad link, we refine the link according to

neuropsychological tests of cognitive capacity and by testing cognitive function during IADL performance.

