## 5.4 Inclusion/Exclusion Criteria

**Table 1. Inclusion/Exclusion Criteria**

Inclusion Criteria	Exclusion Criteria

• Diagnosis of TBI or Ischemic Stroke

• 2-10 years post neurologic event having completed rehabilitation

• Age 18 - 80 years old

• Medically stable

• Fluent in English

• Moderately impaired cognitive function as defined by AMPS Processing sub-scale measures falling below 1.0 logits

• Moderately impaired cognitive capacity as

	

• Have BOTH TBI and Ischemic Stroke

• Intracranial lesions or hemorrhagic stroke

• Other primary neurologic diagnosis

• Any dementia diagnosis

• History of/or symptoms of psychotic spectrum disorders (i.e., bipolar, schizophrenia)

• Persons with alcohol use disorder (AUD) and/or substance use disorder (SUD) diagnoses confirmed by clinical and/or scientific experts

• Reside in an extended care facility

• Less than 2 years post TBI or ischemic stroke

• Anti-epileptic medications for seizure activity

defined by having two or more scores falling $\geq 1$ standard deviation below age normed expectations on: the RBANS index scores, DKEFS Color-Word Trials 3 and 4 scale scores, and/or WAIS-IV Digit Span scaled score	
 
Seizure within the past 3 months or active seizure
 
Contraindications to MRI/iTBS such as ferromagnetic or other magnetic sensitive metals implanted in their head or with in 30cm of the treatment coil or implanted devices in or near the head
 
Medication changes within 3 months of starting participation
 
Currently receiving therapy services
 
Pregnancy
 
FIM scores for problem solving <3 or >4 OR memory <4 or >5, or changes in FIM scores during screening process
 
Neurostimulants that cannot be safely withdrawn
 
Bilateral ischemic stroke
 
Mild or severe impairments in cognitive capacity or cognitive function
 
CHF, implanted pacemakers or defibrillators, or cochlear implants
 
Heart valve with metallic materials
 
Questionable test validity as indicated by DOT (E-score <math>\geq 17</math>) or BRIEF (Negativity <math>\geq 6</math>; Infrequency <math>\geq 3</math>; Inconsistency <math>\geq 8</math>)
 
RBANS Total Scale < 70
 

---	---

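### The telephone screen and the eligibility tables apply opposite logic to the two FIM items, so some Veterans are kept by one rule and excluded by the other

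*Combined protocol and SAP*

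**What the plan says.** Section 5.1, Telephone Screening-Part 2, sets the FIM step over the six months before screening. Its problem-solving condition covers "Veterans requiring minimal or moderate assistance on problem-solving (scores: 3 or 4"). The memory condition is then joined to it in these words: "and/or minimal assistance or supervision on memory (scores: 4 or 5), will remain eligible". The same paragraph gives the purpose: the stepwise approach "will circumvent potential diluting effects of including Veterans at extremes of the functional impairment continuum (mild, severe").

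Section 5.4, Table 1, lists as an exclusion "FIM scores for problem solving <3 or >4 OR memory <4 or >5", together with any change in FIM scores during screening. The optional-study table in Section 5.4 repeats the line.

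Section 2.0 explains the role of the FIM. It is used "to broadly link Veterans according to the FIM category of moderate cognitive impairment", and this broad link is then refined by neuropsychological tests and by observed performance of daily tasks.

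**The concern.** Both rules use the same instrument, the same two items and the same cut-offs, but they join the items differently. The telephone rule admits on one qualifying item. The tables exclude on one non-qualifying item. Screening staff who follow Section 5.1 and a monitor who checks against Section 5.4 would classify the same person differently, which leads to eligibility deviations or uneven enrolment.

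The FIM is the first link that places stroke and TBI Veterans in a common category of moderate impairment, and Aim 1 relies on that common level when it asks whether diagnosis moderates the response. A looser entry rule lets in Veterans with one item outside the moderate range, which works against the stated purpose of the step.

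**Working it through.** The plan gives no figure to reproduce here. The check is one of logic, followed by a count.

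**Inputs.** Problem-solving (PS) in range is 3 or 4, and memory (M) in range is 4 or 5 (Section 5.1, Telephone Screening-Part 2; Table 1 and the optional-study table, Section 5.4). The documents do not state the range of a FIM item, so it is assumed below.

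**The two rules.**
- Telephone: keep if PS is in {3, 4} or M is in {4, 5}.
- Tables: exclude if PS is not in {3, 4} or M is not in {4, 5}. This is the same as keeping only if PS is in {3, 4} and M is in {4, 5}.

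**Test cases.**
- PS 3, M 3: kept by telephone (PS in range), excluded by the tables (M below 4).
- PS 5, M 5: kept by telephone (M in range), excluded by the tables (PS above 4).

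Both cases use only score values that the documents name, so the contradiction does not depend on the assumed range.

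**Count of score pairs.** With k possible scores per item:
- Telephone keeps 2k + 2k − 4 = 4k − 4 pairs.
- The tables keep 2 × 2 = 4 pairs: (3,4), (3,5), (4,4) and (4,5).
- The rules disagree on (4k − 4) − 4 = 4k − 8 pairs, always in the same direction (kept by telephone, excluded by the tables).

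| Assumed range | k | Kept by telephone | Kept by tables | Disagree |
|---|---|---|---|---|
| 3 to 5 | 3 | 8 | 4 | 4 of 8 |
| 2 to 6 | 5 | 16 | 4 | 12 of 16 |
| 1 to 7 | 7 | 24 | 4 | 20 of 24 |

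**How far out of range.** On 1 to 7, the disputed pairs with one item just one point outside are PS 3 or 4 with M 3 or 6 (2 × 2 = 4) and M 4 or 5 with PS 2 or 5 (2 × 2 = 4). That is 8 of the 20. On 2 to 6 it is 8 of 12, and on 3 to 5 it is all 4.

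**Does a later step settle it?** The medical-records step does not mention the FIM. The in-person step lists RBANS, WAIS, DKEFS, BRIEF, Dot Counting and AMPS, but not the FIM. The Table 1 exclusion for changed FIM scores implies that the FIM may be looked at again, but no text says when or under which rule.

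**After either fix.** With 'and' at the telephone screen, 4 pairs are eligible and none conflict. With 'both out of range' in the tables, 4k − 4 pairs are eligible (24 on 1 to 7) and none conflict.

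**The case against.** The strongest reply is that the FIM is only a coarse filter. Section 2.0 calls it a broad link to be refined, and the cohort is fixed in person: at least two neuropsychological scores 1 SD or more under the age norm, RBANS Total Scale not below 70, AMPS Processing below 1.0 logits, and a general exclusion of mild or severe impairment. These apply under either FIM rule, so they limit what reaches the enrolled sample. That stands. It does not make the FIM line redundant. The AMPS criterion has no numeric lower limit, so the FIM range supplies the only numeric floor on everyday function, and the FIM line is a separate exclusion in both tables.

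A second reply is that Section 5.4 is the formal list and later steps may exclude, so a site that applies Table 1 before enrolment would turn the disputed Veterans away. This softens the problem in practice, but no text says that the tables govern. Figure 1, which summarises exclusions by screening step, was not readable in the copy examined and might state the operative rule. Even so, the two written rules would still differ.

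A third reply is to read 'and/or' as a plain 'and'. The sentence giving the basis for the cut-offs refers to the items in the plural, which fits that reading a little better, but it is not the ordinary meaning of the words.

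A reader might infer from 20 of 24 that most Veterans passing the telephone screen are wrongly admitted, or that the looser rule lets in extremes and defeats Aim 1. The documents support neither. The figure counts cells on an assumed scale and gives each pair equal weight. The two items are unlikely to be independent, many disputed pairs are one point out on one item, and the in-person tests still apply.

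**Conclusion.** The contradiction is real as written. It rests only on the ordinary meaning of 'and/or' and on cut-offs printed in both sections. Following the telephone rule as it stands would keep Veterans who already meet a listed exclusion, for the main study and again for the optional study.

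The effect on the sample has unknown size. The share of screened or enrolled Veterans affected cannot be derived from the documents, and the pair counts above show only how the disagreement widens with the assumed score range. The effect on the Aim 1 cohort is limited, though not removed, by the in-person criteria. This is an inconsistency to put right, and it does not invalidate the design.

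**What to change.** State one FIM rule and use it in all three places: Telephone Screening-Part 2 in Section 5.1, Table 1, and the optional-study table in Section 5.4. There are two consistent options:
- Replace 'and/or' with 'and' in the telephone rule. This agrees with the current tables and with the stated aim of keeping out extremes.
- Reword the exclusion in both tables so that it applies only when both items are out of range. This agrees with the current telephone rule.

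The documents do not settle which was intended, so the sponsor should choose, and should check that Figure 1 matches the choice.

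The cost is a short wording amendment. The sample size and the planned analyses do not change. The stricter reading may lower the screening yield, by an amount that the documents do not allow one to estimate.

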***Screening Medical Records:***

The VA electronic medical record and any non-VA medical records will be reviewed to confirm completion of rehabilitation services as indicated by inpatient/outpatient therapy reports and notes. Veterans actively receiving therapy services will be excluded. To examine medical stability, we will also confirm that medical status has remained stable for three months (e.g., new seizures, new diagnoses) prior to the records review as well as absence of other exclusionary conditions (e.g., having both TBI and ischemic stroke). We will also review medications to identify Veterans actively receiving pharmacological neurostimulants. These cases will be reviewed by the study neurologist who will consult with the prescribing physician to determine safe withdrawal, via titration. If there is question about safety, then the Veteran will be

excluded. Dictated radiology reports will be reviewed to identify Veterans with ischemic strokes bilaterally who will be excluded.

**Medication Review:** For participant inclusion and safety, if the participant is prescribed medication known to act on the CNS, an evaluation of cumulative seizure risk and appropriate risk mitigation for each patient according to their prescribed medication profile and relative to self-reported medications, alcohol consumption (AUDIT-C) and substance use (DAST-10) will be evaluated prior to enrollment. In lieu of excluding participants based on the name of any particular drugs or drug classes or limit them to a set, we will follow the procedure as described:

- Clinical experts (e.g., Research Neuropsychiatrist [name], Neuropsychologist [name], Neurologist and Epileptologist [name], Neurologist and Stroke Expert [name]) and/or scientific subject matter experts (e.g., TBI expert [name], AUD and SUD expert [name]) will review all CNS acting medications for each research candidate/participant.
- CNS acting medications will be reviewed for likelihood of seizure risk according to purpose for which the medication was prescribed, dose, speed of dose change (increase or decrease), combination with other CNS active drugs or other factors potentially contributing to lower the seizure threshold (i.e., sleep deprivation, alcohol consumption, marijuana therapeutic and recreational use).
- The determination (by clinical and/or scientific subject matter experts) of likely or plausible seizure risk will be used to make these decisions:
  - To optimize patient safety and mitigate risk, participant should be titrated off a specific medication(s) or receive a lower dose or alternate medication during study participation:
    - If clinical experts determine that the medication(s) can be safely withdrawn or changed, then participant remains eligible.
    - If clinical experts determine that the medication(s) cannot be safely withdrawn or changed, then the participant will be excluded.

To optimize patient safety and mitigate risk, participant should remain on medication as prescribed and remains eligible for study participation.

For Veterans remaining eligible, medical records will be further reviewed to document biological sex, age, time post ischemic stroke or TBI onset and current co-morbid medical conditions. Dictated radiology reports, as well as other records, will be reviewed to document right vs left cortical and sub cortical ischemic strokes and number of ischemic strokes. Radiology reports as well as clinical notes (e.g., History and Physical) will be reviewed to delineate TBI by etiology including diffuse axonal injury (DAI) and  $\geq 1$  contusion (e.g., blast, vehicular, assaults) or DAI +  $\geq 1$  contusion + an anoxic event subsequent to TBI (e.g., respiratory, cardiac). These variables will be examined for use as covariates in analyses.

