### **Motor Threshold Testing & Brain Mapping Site of Stimulation**

Stimulation intensity that will be used in iTBS will be determined by collecting each participant's motor threshold (MT) using the finger representations of the motor cortex. The consensus in the literature is that iTBS can be safely provided at 80% of active motor threshold (AMT). Since there is more within and between subject variability with AMT (e.g, different gripping strengths), relative to resting motor threshold (RMT), scientifically the RMT is preferred. There is also recent evidence that motor threshold estimates using RMT and AMT are equivalent. This means that treatment intensity, based on these two MT estimation procedures, would be equivalent, we will use RMT to estimate MT and compute treatment intensity. Thus, the standard iTBS parameters will be used in this trial to maximize safety. iTBS will be provided at 80% of RMT.

In order to determine motor threshold, a structural brain image of the participant is needed. Therefore, eligible participants will undergo an fMRI scan in order to obtain a structural brain image also referred to as the participant's 3D-MPRAGE T1 volume. This T1 image will be loaded into the Localite TMS Neural Navigator system which is a Magventure compatible and portable neuronavigational system. Based on the T1 image, the right motor cortex will be initially targeted to determine MT. Single pulse TMS will be applied to the optimal scalp location ('hot spot') to activate the abductor pollicis brevis (APB) in the hand, that functions as an abductor of the thumb, on the left hand to determine the RMT, or the lowest stimulus intensity necessary to produce MEPs of peak-to-peak amplitude  $\geq 50\mu\text{V}$  in 5 of 10 subsequent trials. MT is lowest in intrinsic hand muscles and higher in more proximal muscles. The same data will be collected on the opposite hemisphere for comparison measures. MEPs will be recorded using surface EMG electrodes. Data will be stored on the computer for offline analysis. The Magventure C-B60 coil will be used to deliver single TMS pulses for MT determination. All participants, regardless of group randomization will receive MT testing and thus will receive some stimulation. The motor threshold will be measured only at Baseline.

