We will use each Veteran's MT, an indicator of cortical excitability, as the benchmark for determining iTBS intensity for each participant ( iTBS intensity will be 80% of each subject's RMT). This intensity will be maintained throughout study participation.

**iTBS** will be delivered with the Magventure MagProX100 with MagOption stimulator and Cool Coil B65. Active iTBS will be provided using active setting (A) at 80% of each Veteran's resting motor threshold. Placebo iTBS participants will not receive any stimulation as the coil will be switched to placebo (P) setting. To maintain double-blind in A and P settings, Veterans and researchers wear headphones connected to a sham noise generator.

For **APT**: 30 min of training exercises, 10 min metacognitive training, and 5 min of functional goal setting. Study-Days 2 or 3 sessions will each include novel exercises. For metacognitive training, the Veteran will be instructed on how to use strategies to self-regulate or to "think about his or her own thinking" and to self-monitor while performing an activity and efficiently allocate his or her cognitive resources. Goals will then be set to implement the strategy in the Veteran's daily life.

**iTBS** will be delivered with the Magventure MagProX100 with MagOption stimulator and Cool Coil B65. Active iTBS will be provided using active setting (A) at 80% of each Veteran's resting motor threshold. Participants randomized to active iTBS will receive stimulation at the left DLPFC at 80% RMT. 80% RMT is the intensity most commonly used and cited in the literature and has been shown to be safe. The right DLPFC will be marked in the TMS Localite

Navigation system for each participant. The navigation system will provide target guidance and will help the researcher to position the coil very precisely in reference to the participant's brain. The neuronavigation system will be used every iTBS session to ensure reproducibility and consistency at the stimulation site.

For the Optional Study: The site of stimulation will be determined by the GIMME modeling. Optimal brain target is identified through GIMME modeling, which is a directed functional connectivity modeling approach based on iterative model optimization.

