*EEG:* For participant safety, all participants will complete a 30-minute baseline EEG sampling. EEG will not be routinely repeated unless clinically indicated. The EEGs will be interpreted by Epileptologists to confirm absence of seizure activity (i.e., epileptiform discharges).

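### The Medication Review allows CNS drug changes that Table 1 would exclude; if the review governs, the once-only motor threshold that sets the iTBS dose can reflect a different drug state from the treatment session

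*Combined protocol and SAP*

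**What the plan says.** **Drug changes.** The Medication Review (section 5.1, Screening Medical Records) provides that a participant may be "titrated off a specific medication(s) or receive a lower dose or alternate medication during study participation". The eligibility test is a judgement about feasibility: if the drug "can be safely withdrawn or changed, then participant remains eligible". The evaluation is placed before enrollment. Nothing there says when the change itself must be finished.

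**Stability.** Table 1 in section 5.4, and the matching table for the optional study, exclude anyone with a medication change in the 3 months around starting participation. Neither table defines that start or mentions changes the study directs. The same tables exclude neurostimulants only where they cannot be withdrawn safely, so withdrawal for the study is evidently foreseen.

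**Dose.** The motor threshold is "an indicator of cortical excitability, as the benchmark for determining iTBS intensity for each participant" (Motor Threshold Testing & Brain Mapping Site of Stimulation). That section states "The motor threshold will be measured only at Baseline". iTBS is set at 80% of the resting value, and "This intensity will be maintained throughout study participation".

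**EEG.** On Study-Day 1 a physician must review the EEG before motor threshold testing. Section 5.5 adds: "EEG will not be routinely repeated unless clinically indicated".

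**The concern.** The two eligibility rules lead to different participants and different timetables. If Table 1 governs, a change made before the start implies a 3-month wait that the Medication Review never mentions. If the Medication Review governs, a Veteran can be mid-taper, or newly on another drug, between the Study-Day 1 tests and an iTBS session.

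The second case matters on the protocol's own reasoning. It treats motor threshold as a marker of cortical excitability, and it tells the experts to weigh how fast a dose is raised or lowered when judging seizure risk. A drug change after the threshold is taken could therefore leave the dose away from the intended 80%. If the threshold has fallen, the session is stronger than the intensity chosen for safety, in a population whose seizure risk from iTBS the device-exemption text in section 5.1 calls unknown. If it has risen, the active session is weaker than intended. Because "Placebo iTBS participants will not receive any stimulation", that weakening could only dilute the Active versus Placebo contrasts planned under Aim 2.

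**Working it through.** The main check is a reading of the rules side by side. The arithmetic only shows how far a fixed dose could drift.

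1. **Does any rule order the change before the tests?** Table 1 does so indirectly if read literally, since a change made before the start would have to be at least 3 months old. The Medication Review keeps the Veteran eligible on a finding that the change can be made. The Study-Day 1 schedule puts EEG before motor threshold but ties neither to a finished drug change. The 3-month filter at list extraction precedes the review, so it cannot catch changes the review orders.

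2. **Can the review fall late?** It draws on AUDIT-C and DAST-10, which are completed at the in-person visit (Study-Day 0). A change that relies on those scores follows Day 0, and no interval from Day 0 to Day 1 is given.

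3. **Is there a second route to a drug change after baseline?** Yes. The rescheduling rules let a participant who reports taking CNS stimulants agree to stop them and continue. No new motor threshold or EEG is specified for that case.

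4. **How long does one threshold serve?** From the study-day schedule, counted from Study-Day 1 (nominal, since Day 1 may be split over two days):
   - Study-Day 2: 4 days
   - Study-Day 3: 4 + 14 = 18 days
   - Study-Day 4: 18 + 14 = 32 days, with no iTBS
   - Optional Day 5 (TBI only): 32 days, up to 32 + 14 = 46 days

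5. **What would a shift do to the dose?** Let d be the relative change in resting motor threshold after baseline. The delivered intensity as a percentage of current threshold is 80 / (1 + d). With d = 0 this returns the plan's 80%. The documents give no value for d, so the range below is an assumption:
   - d = -20%: 80 / 0.80 = 100.0%
   - d = -10%: 80 / 0.90 = 88.9%
   - d = -5%: 80 / 0.95 = 84.2%
   - d = +5%: 80 / 1.05 = 76.2%
   - d = +10%: 80 / 1.10 = 72.7%
   - d = +20%: 80 / 1.20 = 66.7%

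6. **How many Veterans?** Not stated. Each one in the Active arm is 1 / 24 = 4.2% of that arm.

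**The case against.** The strongest reply is that the harm needs a reading no sentence states. Table 1 has no exemption, so taken literally it already keeps recent changes out. The reference to study participation in the Medication Review may describe the drug state to be held while on study, not the time at which to taper. The evaluation precedes enrollment, Day 0 is called the final screening step, and with no fixed gap to Day 1 nothing stops the team from finishing a taper first. The stated consequences of the AUDIT-C and DAST-10 scores are exclusion, referral or monitoring; a taper prompted by them is an inference from their use in the review. Clinical experts, including an epileptologist, assess each case, safety indicators are tracked every study day, and any seizure pauses treatment.

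Most of this stands, and it rules out some stronger readings. A reader might infer that nothing in the protocol could force a change to be complete before testing; Table 1, read literally, could. A reader might infer that the EEG can never be repeated; it can when clinically indicated. A reader might also see a clash with the stopping rule on mental-health medication. That rule concerns changes during participation and, for doses, changes made for mental health reasons. A swap ordered for seizure risk before the start need not meet it.

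What the reply does not remove is the conflict itself. The literal Table 1 reading sits badly with a review that keeps changed Veterans eligible, and expert judgement cannot stand in for a re-measurement that the text restricts to baseline. The motor threshold has no clinical-indication exception of the kind the EEG has.

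**Conclusion.** The concern holds as a conflict between two stated rules, with a consequence for dosing and safety. The protocol does not say whether the Medication Review or the Table 1 exclusion governs a change the study orders. If the review governs, the fixed dose and the routine EEG clearance may belong to a different drug state from the session.

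The size is open. The illustrative 66.7% to 100% range rests wholly on an assumed threshold shift of up to 20% either way, and the number affected could be zero. A reader might infer that mis-dosing confined to the Active arm biases the randomised comparison in a way randomisation cannot handle. The documents do not support that: randomisation balances in expectation who has a drug change, and imprecise active dosing is possible dilution, not confounding. The point deserves a protocol edit because the correction is cheap and follows from the protocol's own account of seizure risk and excitability.

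**What to change.** Three edits:

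1. **Table 1 and the optional-study table.** Keep the 3-month exclusion for all other changes. Add: *Changes ordered by the study medication review are allowed if complete and stable, for an interval the clinical experts record for that Veteran, before the Study-Day 1 EEG and motor threshold.*
2. **Medication Review.** Replace the timing phrase that ends the titration sentence with: *before Study-Day 1 and for the rest of study participation.*
3. **Motor Threshold Testing.** After the baseline-only sentence add: *If a CNS-acting drug is changed after Study-Day 1 and the participant continues, motor threshold is re-measured and the epileptologist decides on a repeat EEG before the next iTBS session.* This also covers stimulants stopped under the rescheduling rules.

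The cost is a longer gap between Day 0 and Day 1 for Veterans whose drugs are changed, and a rare repeat motor threshold using the stored T1 image. Their Day 0 eligibility scores may predate the change, but the first persisting-effects battery (B0, Study-Day 2) would follow it. For these Veterans the first edit replaces a literal 3-month wait with an expert-set interval, which is why the interval should be recorded. If the sponsor prefers the full 3 months, the Medication Review should say so; the third edit is needed either way.
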